16.7.2.2. Handling of Missing Data for Statistical Analysis

For the joint model, missing baseline data will be modelled as part of the MCMC sampling, no post baseline data will be imputed. For all other models, missing data will not be imputed.

16.7.2.3. Handling of Missing Data for PK Analysis

GSK standards for handling missing PK data will be applied to all PK outputs.

16.8. Appendix 8: Values of Potential Clinical Importance

16.8.1. Laboratory Values - Haematology

Haematology parameters will use CTCAE grades (CTCAE criteria, V4.03: June 14, 2010) to highlight important results based on laboratory value only (i.e. no clinical judgement will be applied). CTCAE grades will replace the category of "values of potential clinical importance" for haematology parameters, see table below for reference.

	CTCAE v4.03				
	Adverse				
Parameter	Event	Grade 1	Grade 2	Grade 3	Grade 4
Haemoglobin	Anemia	Hemoglobin (Hgb) <lln -="" 100
g/L</lln>	Hgb <100 - 80g/L	Hgb <80 g/L; transfusion indicated	Life-threatening consequences; urgent intervention indicated
Haemoglobin	Hemoglobin increased	Increase in >0 - 20 g/L above ULN or above baseline if baseline is above ULN	Increase in >20 - 40 g/L above ULN or above baseline if baseline is above ULN	Increase in >40 g/L above ULN or above baseline if baseline is above ULN	_
	Haptoglobin				
Haptoglobin	decreased	<lln< td="">-	-	-	</lln<>	-	-	-
Lymphocyte count	Lymphocyte count decreased	<lln -="" 0.8
GI/L</lln>	<0.8 - 0.5 GI/L	<0.5 - 0.2 GI/L	<0.2 GI/L
Lymphocyte count	Lymphocyte count increased	-	>4 - 20 GI/L	>20 GI/L	-
Neutrophil count	Neutrophil count decreased	<lln -="" 1.5
GI/L</lln>	<1.5 - 1.0 GI/L	<1.0 - 0.5 GI/L	<0.5 GI/L
Platelet	Platelet count	<lln -="" 75.0<="" td=""><75.0 -	<50.0 - 25.0		</lln>	<75.0 -	<50.0 - 25.0	
Count White blood cell count	decreased		50.0 GI/L	GI/L >100 GI/L	<25.0 GI/L Clinical manifestations of leucostasis; urgent intervention indicated
White blood cell count	White blood cell decreased	<lln -="" 3.0
GI/L</lln>	<3.0 - 2.0 GI/L	<2.0 - 1.0 GI/L	<1.0 GI/Lp

201247

16.8.2. Laboratory Values – Chemistry and Liv	er
---	----

Clinical Chemistry						
Laboratory Parameter	r Units Category Clinical Concern Range			ncern Range		
			Low Flag (< x)	High Flag (>x)		
Albumin	G/L		30			
Calcium	mmol/L		2	2.75		
Creatinine	µmol/L	Δ from BL		↑ 44.2		
Glucose	mmol/L		3	9		
Potassium	mmol/L		3	5.5		
Sodium	mmol/L		130	150		

Liver Function					
Test Analyte	Units	Category	Clinical Concern Range		
ALT (SGPT)	U/L	High	\geq 2x ULN		
AST (SGOT)	U/L	High	\geq 2x ULN		
Alkaline Phosphatase	U/L	High	\geq 2x ULN		
T Bilirubin	µmol/L	High	≥ 1.5xULN		
	µmol/L		1.5xULN T. Bilirubin		
T. Bilirubin + ALT		High	+		
	U/L		\ge 2x ULN ALT		

16.8.3. ECG

ECG Parameter	Units	Clinical Concern Range					
		Lower	Upper				
Absolute							
Absolute QTc Interval	msec		>530				
Absolute PR Interval	msec	< 110	> 220				
Absolute QRS Interval	msec	< 75	> 110				
Change from Baseline	Change from Baseline						
Increase from Baseline QTc	msec		> 60				
'QTc' (corrected QT interval) may be recorded as QTcF, QTcB or another method documented in the SI code list. These limits should be applied to both QTcF, QTcB (which will be primary output variables) and alternative QTc methods (which will be listed where relevant)							

201247

16.8.4. Vital Signs

Vital Sign Parameter	Units	Clinical Concern Range		
(Absolute)		Lower	Upper	
Systolic Blood Pressure	mmHg	< 85	> 160	
Diastolic Blood Pressure	mmHg	< 45	> 100	
Heart Rate	bpm	< 40	> 110	

Vital Sign Parameter	Units	Clinical Concern Range
(Change from Baseline)		An increase or decrease from baseline of the following magnitude
Systolic Blood Pressure	mmHg	≥ 40
Diastolic Blood Pressure	mmHg	≥ 20
Heart Rate	bpm	≥ 30

16.9. Appendix 9: Population Pharmacokinetic (PopPK) Analyses

The details of the PopPK model are specified in Appendix 10 (PopPK/PD model). The first intent is to simultaneously estimate the parameters of the PopPK/PD model, using total GSK2330811 and Total OSM data. If a sequential modelling approach (i.e. PopPK model and PK/PD separately) is required, the principles and details specified in Appendix 10 will apply to the PopPK model. Appendix 10

16.9.1. Pharmacokinetic / Pharmacodynamic Dataset Specification

Pharmacokinetic / Pharmacodynamic Dataset Specification

NONMEM dataset 1: PK/PD

- To support both the PK and the PK/PD analyses a NONMEM dataset will be generated
- The population PKPD dataset will be used for both the PK and the PK/PD analysis selecting the rows which apply.
- It will be a comma delimited text file, named <"NM.GSK2330811.201247.PKPD.v1.csv">.
- This file will include events of dosing or concentration as rows, with the variables in the table below as columns. Rows will be in increasing order of unique subject identification number; and all events in the same subject must be consecutive and in chronological order, ending with the last concentration event (i.e. dosing events that occur after the last quantifiable concentration in a subject will not be included in the data file).
- All plasma and blister fluid GSK2330811 and PD (free and total OSM in blister and serum) will be included (i.e. all scheduled and unscheduled visits).
- Non-numerical concentration values (such as missing samples, not assayed samples or non-reportable samples) will not be included. Subjects with non-quantifiable concentration values will be included.

Name	Implicit Unit	Description	Derivation	Format
ID	-	Unique subject identification number	PKCNC.SUBJID for concentration events and EXPOSURE.SUBJID for dosing events.	Numeric
TRFD	Н	Event time from first dose	(PKCNC.PCSTDM – MSTONE.MSTSTDM)/3600 for PK concentration events. Similarly for PD concentration events and EXPOSURE.EXSTDM – MSTONE.MSTSTDM)/3600 for dosing events. Rounded to 2 decimal places.	Numeric
DV	PK: ng/mL PD: pg/ml for OSM	For concentration events: plasma and blister fluid concentration of GSK2330811, OSM free and total in serum and blister. For dosing events: 0	PKCNC.PCSTRESN for PK concentration events (similarly for PD concentration events). "0" for dosing events. "0" for non- quantifiable concentrations BIOMARK.BIORESN for BITESTCD=	Numeric

201247

Name	Implicit Unit	Description	Derivation	Format
			CONCTSZ (Normal Activity) for OSM	
BQL		Below limit of quantification concentrations	1 for non-quantifiable concentrations, 0 otherwise Note: LLQ=100ng/mL for GSK2330811; LLQ=1.4pg/mL for Free and Total OSM	numeric
AMT	mg	For dosing events: dose of GSK2330811. For concentration events: 0	For dosing events (i.e. EVID=1): 0 for subjects on Placebo and dose for subjects on GSK2330811. For concentration events (i.e. EVID=0) AMT=0.	numeric
MDV	-	For concentration events: 0 For non-quantifiable concentration values: 0. For dosing events: 1	Hard coded as description (1 if data is from EXPOSURE; 0 if PKCNC.PCSTRESN or PD is not missing; 0 if PCSTRESN is missing and PCORRES is not missing, i.e. non-quantifiable sample).	Numeric
EVID		For DOSE events: 1, for concentration events: 0		
СМТ	-	Compartment: For dosing events 1, for PK concentration events: 2. For PD concentration events: 4 and 5.	1 in records with LABL= "DOSE". 2 in records with LABL= "PK". 4 in records with LABL= "PD" and ASSAY_NAME="Free Oncostatin M". 5 in records with LABL= "PD" and ASSAY_NAME="Total Oncostatin M"	Numeric
NOMT	Н	Planned PK sample time relative to dose For dosing events: 0 For pre-dose concentration events: 0	Extract numeric part of PKCNC.PTM (or format PTMNUM). Similarly for PD. For dosing events = "0"	Numeric
DAY	-	Study day	PKCNC.PCACTSDY for concentration events (similarly for PD) and EXPOSURE.EXACTSDY for dosing events.	Numeric
VIS	-	Visit number	PKCNC.VISITNUM (visit sequence number) for PK events (similarly for PD) and EXPOSURE.VISITNUM for dosing events.	Numeric
DOSE	mg	Dose of GSK2330811 in mg (for all events)	AMT added to all records	Numeric
STUD	-	Numeric part of study identifier (i.e. 201247)	201247 for all records	Numeric
BASELINE	Same unit of DV for each	0 if LABL_NAME="PK" and "DOSE", baseline		Numeric

201247

Name	Implicit Unit	Description	Derivation	Format
	ASSAY_NAME	otherwise		
SEX		Subject gender	1 for males and 2 for females	Numeric
WT	kg	Body weight at baseline visit	VITALS.WEIGHT at baseline visit.	Numeric
BMI	kg/m2	Body mass index at baseline visit	VITALS.WEIGHT/(VITALS.HEIGH T/100)^2	Numeric
HT	cm	Height at baseline visit	VITALS.HEIGHT	Numeric
DATE	-	Date of event	For dosing events, EXPOSURE.EXSTDT. For PK events, PKCNC.PCSTDT. Similarly for PD.	DD/MM/YYYY
TIME	-	Clock time of event	For dosing events, EXPOSURE.EXSTTM. For PK events, PKCNC.PCSTTM. Similarly for PD.	HH:MM
LLQ	-	Lower Limit of Quantitation		Numeric
FLAG		1 to 7	1 in records with LABL= "DOSE". 2 in records with LABL= "PK" and MATRIX_NAME="Plasma". 3 in records with LABL= "PK" and MATRIX_NAME="Blister Fluid". 4 in records with LABL= "PD" and ASSAY_NAME="Free Oncostatin M" and MATRIX_NAME="serum". 5 in records with LABL= "PD" and ASSAY_NAME="Total Oncostatin M" and MATRIX_NAME="Serum". 6 in records with LABL= "PD" and ASSAY_NAME="Free Oncostatin M" and MATRIX_NAME="Serum". 6 in records with LABL= "PD" and ASSAY_NAME="Free Oncostatin M" and MATRIX_NAME="Blister Fluid". 7 in records with LABL= "PD" and ASSAY_NAME="Total Oncostatin M" and MATRIX_NAME="Blister Fluid".	numeric
REGIMEN		Regimen sort order		numeric
COHORT		Cohort sort order		numeric
LABL_NAM E	-	Record label	VARCHAR2(32) Maximum 32 characters (numeric or text), Record identifier: In dosing records: "DOSE" In PK concentration records "PK"	varchar

201247

Name	Implicit Unit	Description	Derivation	Format
			in PD concentration records "PD"	
ASSAY_NA ME	-	Used assay	In records with LABL="DOSE" and "PK", use "PK_assay" In records with LABL="PD" use the appropriate assay: "OSM free etc"	varchar
MATRIX_N AME		Used matrix (i.e. "plasma", "serum", "blister")		varchar
MRSS		mRSS score		numeric

Dataset 2: PK/PD and Haematology

The dataset will include exposure, total OSM, Platelets (PLT), Red Blood Cells (RBC), Reticulocytes (RET), Haemoglobin (Hb), Immature reticulocyte fraction, Reticulocytes (percentage/ratio), erytropoyetin (EPO) and thrombopoietin (TPO)

- An additional dataset will be generated to support graphical analyses for haematology biomarkers
- It will be a comma delimited text file, named eda-gsk2330811-201247-pkhaem.csv.
- This file will include time of visits as rows, with the variables in the table below as columns. Rows will be in increasing order of unique subject identification number; and all events in the same subject must be consecutive and in chronological order.
- if any variable is missing at a certain time, assign NA.
- All scheduled and unscheduled visits will be included for plasma GSK2330811, serum Total OSM and haematology (Platelets, Red Blood Cells, Reticulocytes, Haemoglobin, Immature reticulocyte fraction, Reticulocytes (percentage/ratio), EPO, TPO). Only central labs readings will be included.
- Non-numerical concentration values (such as missing samples, not assayed samples or non-reportable samples) will not be included. Subjects with non-quantifiable concentration values will be included.

Pseudocode:

Select SUBJID, ELTMSTN, PCSTRESN, PCACTSDY, VISITNUM, PCSTDT from PKCNC where PKCNC.PCSPEC='Plasma'. There should be one record per subject per visit.

Rename NOMT=ELTMSTN, DAY= PCACTSDY, DATE=PCSTDT

Select SUBJID, ATRGDY, BISTRESN, BIACTDY, VISITNUM, BIDT from BIOMARKER where BICATCD in ('TOSM') and AVISIT is not 'DAY 1'. There should be one record per subject per visit.

Mutate ATRTGDY= ATRGDY-1

Rename NOMT=ATRTGDY, DAY=BIACTDY, DATE=BIDT

201247

Select SUBJID, AVISIT, LBSTRESN, LBACTDY, VISITNUM, BIDT (please verify if this is the date information) from LABHAEM where LBTESTCD in ('PLT_BLC', HB_BLC, RBC_BLC, RETIC_BLC, IRF_BLQ, RETIC_BLQ, EPO_PLC, THROMB_PLC)

Calculate NOMT as follow: if AVISIT='BASELINE' then NOMT=0 else NOMT=(numerical part of AVISIT). Drop AVISIT. Rename DAY= LBACTDY, DATE=BIDT

Transpose records by SUBID, NOMT DAY, DATE, VISITNUM (var=LBSTRESN, id= LBTESTCD) so that there is one record per subject per visit. Each variable in LBTESTCD will be a column.

Join selected PKCNC and BIOMARKER records by SUBJID, NOMT, DAY, DATE

Join with LABHAEM dataset by SUBJID, NOMT, DAY, DATE

Select SUBJID, and information on DOSE, SEX, WT, BMI, HT, REGIMEN and COHORT from appropriate dataset and Join by SUBJID

Name	Implicit Unit	Description	Derivation	Format
SUBJID	-	Unique subject identification number		Numeric
NOMT	h	Planned sample time relative to dose		Numeric
CONC	ng/mL	GSK2330811 plasma concentration	PKCNC.PCSTRESN where PKCNC.PCSPEC='Plasma' if PKCNC.PCSTRESC='NQ' then CONC=0 if >1 observation at same date/time. take the mean.	numeric
TOSM	pg/mL	Total OSM serum concentration	BIOMARK.BISTRESN where BICATCD in ('TOSM') and AVISIT is not 'DAY 1' if >1 observation at same date/time, take the mean.	
PLT	1E9/L	platelet count	LBSTRESN where LBTESTCD in ('PLT_BLC')	
Name	Implicit Unit	Description	Derivation	Format
--------	---------------	------------------------------------	--	--------
НВ	g/L	haemoglobin	LBSTRESN where LBTESTCD in ('HB_BLC')	
RBC	TI/L	red blood cells	LBSTRESN where LBTESTCD in ('RBC_BLC)	
RETIC	TI/L	reticulocytes	LBSTRESN where LBTESTCD in ('RETIC_BLC')	
IMRETF		immature reticulocyte fraction	LBSTRESN where LBTESTCD in ('IRF_BLQ')	
RETPR	ratio	reticulocyte (percentage/ratio)	LBSTRESN where LBTESTCD =' RETIC_BLQ'	
EPO		erithropoietin	in clinical chemistry Ibtestcd="EPO_PLC".	
TPO	ng/L	thrombopoietin	LBSTRESN where LBTESTCD =' THROMB_PLC'	

201247

Name	Implicit Unit	Description	Derivation	Format
DAY	-	Study day		Numeric
VISITNUM	-	Visit number		Numeric
DATE	-	Date of event		DD/MM/YYYY
DOSE	mg	Dose of GSK2330811 in mg		Numeric
SEX		Subject gender	1 for males and 2 for females	Numeric
WT	kg	Body weight at baseline visit	VITALS.WEIGHT at baseline visit.	Numeric
BMI	kg/m2	Body mass index at baseline visit	VITALS.WEIGHT/(VITALS.HEIGH T/100)^2	Numeric
HT	cm	Height at baseline visit	VITALS.HEIGHT at baseline	Numeric
REGIMEN		Regimen sort order		numeric
COHORT		Cohort sort order		numeric

Dataset 3: PK and Clinical efficacy and biomarkers

The dataset will include exposure-related parameters and clinical efficacy and biomarker endpoints. The dataset will be required after SAC, based on the results of the statistical analysis.

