10.3.2. Other Analyses

PK, pharmacodynamic and biomarker exploratory analyses will be described in the RAP.

The analysis approach for exploratory biomarkers will be:

- Relationships between endpoints, explored graphically and using statistical measures of consistency if data allow.
- Profiles / Trends over time of individual endpoints

- Inference using posterior probabilities of the true within participant change from baseline and true between group treatment difference using non-informative prior distributions.

In addition to the univariate analysis of the change from baseline in each biomarker, a multivariate analysis of endpoints of several biomarkers of fibrosis may also be performed.

The primary between-group analysis will be between the placebo and GSK2330811 groups. However if a difference in baseline levels of key biomarkers of fibrosis is observed by mycophenolate use then an alternative primary comparison will be considered.

The following PK/PD analyses will be conducted if data permit:

- To examine the relationship between plasma concentrations of GSK2330811, and target OSM concentration (total).
- To examine the relationship between plasma concentrations of GSK2330811, and platelet count.

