16.3. Appendix 3: Assessment Windows

Following visit windows are applied for early withdrawal and unscheduled visits. The target day is the planned analysis timepoint and windows have been constructed with limits approximately equally spaced between visits. If more than one values within analysis timepoint with equal distance from the target day then average will be used.

Table A:

Domain	Analysis Window	Analysis	
	Beginning Timepoint	Ending Timepoint	Timepoint
All	Day 1	Day 1	Day 1
Vital Signs, Standard	Day 8	Day 22	Day 15
Haematology/Clinical Chemistry	Day 23	Day 36	Day 29
	Day 37	Day 50	Day 43
	Day 51	Day 64	Day 57
	Day 65	Day 78	Day 71
	Day 79	Day 99	Day 85
	Day 100	Day 134	Day 113
	Day 135	Day 176	Day 155
	Day 177	> Day 197	Day 197
Additional Haematology, Urinalysis,	Day 68	Day 99	Day 85
Laboratory FVC, SHAQ-VAS, HAQ-DI, PhGA, PtGA and CRISS	Day 145	> Day 197	Day 197
Immature Reticulocyte Fraction	Day 37	Day 50	Day 43
	Day 68	Day 99	Day 85
	Day 145	> Day 197	Day 197
ECG	Day 8	Day 22	Day 15
	Day 50	Day 64	Day 57
Target Engagement (OSM)	Day 8	Day 22	Day 15
	Day 23	Day 43	Day 29
	Day 50	Day 64	Day 57
	Day 78	Day 92	Day 85
	Day 108	Day 120	Day 113
	Day 145	Day 165	Day 155
	Day 187	> Day 197	Day 197
Blood Biomarkers	Day 15	Day 43	Day 29
	Day 44	Day 71	Day 57
	Day 72	Day 99	Day 85
	Day 145	> Day 197	Day 197
CRP	Day 8	Day 22	Day 15
	Day 23	Day 43	Day 29
	Day 44	Day 71	Day 57

201247

Domain	Analysis Window	Analysis	
	Beginning Timepoint	Ending Timepoint	Timepoint
	Day 72	Day 99	Day 85
	Day 100	Day 127	Day 113
	Day 145	> Day 197	Day 197
mRSS	Day 43	Day 71	Day 57
	Day 72	Day 99	Day 85
	Day 145	> Day 197	Day 197
Skin Biopsy	Day 55	Day 99	Day 85
Home FVC ^[1]	Day 5	Day 11	Day 8
(Target visit -/+ 3 days)	Day 12	Day 18	Day 15
	> Day 194		Day 197

[1] Steps for Home FVC Slotting

- Step 1: Select maximum value within a day.
- Step 2: After slotting, select the closest target day.
- Step 3: If more than one value within the analysis timepoint with equal distance from the target day, the 'average of maximum value' will be used.

For PK, planned assessments will be summarised, unscheduled assessments will be listed. PopPK and PK/PD modelling will use all available data and will use actual relative time, not planned relative time.

Note: Following assessment window followed for all SRT reporting.

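### In SAP Dataset 2 the join key for total OSM runs one day behind the key for haematology, so post-baseline values would fall on separate rows if laboratory visits are labelled by study day

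*SAP*

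**What the plan says.** SAP 16.9.1, under Dataset 2 (PK/PD and Haematology), gives pseudocode that builds one file from three sources. Each source gets its planned time, NOMT, in a different way:

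- Plasma concentration: "Rename NOMT=ELTMSTN, DAY= PCACTSDY, DATE=PCSTDT". The unit of ELTMSTN is not given.
- Total OSM: "Mutate ATRTGDY= ATRGDY-1", followed by "Rename NOMT=ATRTGDY, DAY=BIACTDY, DATE=BIDT".
- Haematology: "if AVISIT='BASELINE' then NOMT=0 else NOMT=(numerical part of AVISIT", with nothing subtracted.

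Concentration and OSM are first joined on subject, NOMT, day and date. The last step is "Join with LABHAEM dataset by SUBJID, NOMT, DAY, DATE". All four keys must agree for values to share a row.

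The same section asks for one record per participant per visit in each source, with NA where a variable is absent at a given time. Its variable table gives the unit of NOMT as h. The laboratory step takes its date from BIDT, the variable also used for OSM, and carries a bracketed request to check that this is right.

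**The concern.** The laboratory rule is inconsistent within itself. It sets baseline to 0, which is the origin of a day-minus-1 scale, but leaves later visits on the study-day scale. The OSM rule is on the day-minus-1 scale throughout. Because NOMT is a join key, a one-day offset is enough to stop two measurements from the same visit sharing a row.

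The failure could also pass unremarked. Under the NA rule, a failed join looks the same as a value that was never collected. Anyone plotting OSM against platelets row by row would find no post-baseline pairs. Anyone plotting against NOMT would see the two series one nominal day apart.

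**Working it through.** The SAP states no count of matched rows, so there is no figure to reproduce. The check is to apply the stated rules to one participant with a complete schedule.

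**Inputs**

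- Post-baseline OSM visits: Days 15, 29, 57, 85, 113, 155 and 197 (SAP Appendix 2 schedule; Appendix 3, Table A). Plasma concentration has the same seven.
- Post-baseline standard haematology visits: the same seven plus Days 43 and 71, nine in all.
- Label scale: Table A labels both domains by study day and says "The target day is the planned analysis timepoint and windows have been constructed with limits approximately equally spaced between visits". The OSM step of the pseudocode also uses a day label: "BICATCD in ('TOSM') and AVISIT is not 'DAY 1".
- Assumption: laboratory AVISIT carries these study-day labels. The SAP does not show the labels themselves.

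**Step 1: NOMT by source, for a visit on day d**

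- OSM: d − 1, giving 14, 28, 56, 84, 112, 154, 196.
- Haematology: d, giving 15, 29, 43, 57, 71, 85, 113, 155, 197.

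Every OSM value is even and every laboratory value is odd, so the two sets have nothing in common. Since DAY and DATE must match as well, only records from the same visit could join, and within a visit d − 1 never equals d. The result is 0 of 7 shared visits. It follows that no post-baseline row can hold all three sources, whatever the scale of ELTMSTN.

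**Step 2: row counts and alternative readings**

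An inner join gives no post-baseline rows. An outer join, which the NA rule implies, gives these counts per participant:

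| Reading | Post-baseline rows | OSM with haematology | PK with OSM | PK with haematology |
|---|---|---|---|---|
| As written, ELTMSTN in days minus 1 | 7 + 9 = 16 | 0 | 7 | 0 |
| As written, ELTMSTN in hours | 7 + 7 + 9 = 23 | 0 | 0 | 0 |
| Laboratory labels by week, ELTMSTN in days minus 1 | 16 | 0 | 7 | 0 |
| Laboratory NOMT reduced by 1, ELTMSTN in days minus 1 | 9 | 7 | 7 | 7 |
| Laboratory NOMT reduced by 1, ELTMSTN in hours | 7 + 9 = 16 | 7 | 0 | 0 |

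With week labels the number 28 appears in both sources, but it is Day 29 for OSM and Week 28 (Day 197) for the laboratory. DAY and DATE block that match.

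The footnotes to SAP Table 4.1 and the PK figures place trough samples at Day 14 to Day 84, which is the day-minus-1 scale. That suggests the subtraction was meant to align OSM with PK, and that the laboratory step was left behind. It does not settle the unit of ELTMSTN.

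**Step 3: baseline**

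A baseline OSM record with target day 1 gets 1 − 1 = 0, which equals the laboratory baseline value of 0. Baseline therefore joins if such a record survives the filter on DAY 1, and does not if DAY 1 is the only label it carries.

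**The case against.** The strongest reply is that the deciding input is missing. The laboratory AVISIT labels are not shown, and the laboratory source uses BASELINE where the OSM source uses DAY 1, so the two need not share a convention. If laboratory labels were already on the day-minus-1 scale (Day 14, Day 28), the pseudocode would work as it stands and a further subtraction would break it. This stands as a condition on the finding. Table A makes study-day labels the likely case, and nothing in the SAP shows day-minus-1 labels for laboratory data.

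Four stronger readings are tempting, and the documents do not support them:

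- **Data are lost.** The NA rule implies an outer join. Every value stays in the file with its own day and date, so pairs can be rebuilt.
- **Baseline OSM is dropped.** The filter may only remove a duplicate of a BASELINE record. The SAP does not say, so this is a point to confirm.
- **Concentration cannot be paired with haematology.** That depends on the unstated unit of ELTMSTN. If it held the unshifted visit day, concentration would match haematology and miss OSM.
- **A protocol aim fails.** Protocol 10.3.2 includes the aim "To examine the relationship between plasma concentrations of GSK2330811, and platelet count". SAP Section 12 and Appendix 10 assign exposure-response for platelets and haemoglobin to a separate pooled analysis. Figures 4.7, 4.8, 6.5 and 6.6 show related comparisons within this study and are not said to use Dataset 2.

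It is also fair to say that this is pseudocode, visibly unfinished, and that a programmer may notice the split rows on the first run. That lowers the consequence but does not make the written rule right.

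**Conclusion.** The rule as written is inconsistent. If laboratory AVISIT carries Table A's study-day labels, 0 of 7 shared post-baseline visits would hold total OSM and haematology in one row. Each of those visits would be split over at least two rows padded with NA, contrary to the intended one record per visit. Post-baseline rows per participant would be 16 instead of 9 if ELTMSTN is on the day-minus-1 scale, or 23 if it is in hours. In both of those cases concentration misses haematology as well.

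The effect is limited to the exploratory graphical file. The primary endpoints, the Bayesian models and the OSM/PK model, which uses Dataset 1, do not depend on it. Nothing in the SAP has the pooled exposure-response analysis drawing on it. This is a minor correction to a programming specification.

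**What to change.** 1. Confirm the laboratory AVISIT labels. If they are study days, set laboratory NOMT to the numerical part of AVISIT minus 1 after baseline, and keep 0 at baseline.
2. State the unit of ELTMSTN, and convert it to days on the same scale if it is in hours. Correcting the laboratory rule alone would still leave concentration unmatched in that case.
3. Change the unit of NOMT in the Dataset 2 variable table from h to days.
4. Resolve the open query on the laboratory date variable, since DATE is itself a join key.
5. Confirm that exactly one baseline OSM record per participant remains after the DAY 1 filter. Simply lifting the filter could duplicate baseline.

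With steps 1 and 2 done, all 7 shared visits hold the three sources together, in 9 post-baseline rows per participant. Joining on subject and date alone is less clean: it leaves conflicting NOMT values to reconcile and relies wholly on the date field that still needs checking.

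The cost is a few lines of the dataset specification and a look at the source labels. No data collection, model or planned display changes.
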